
among treatment features will be calculated in patient-specific utilities or part-worths associated with the attribute levels in the study. For other outcomes, participants will receive the following surveys via mail within 1-2 weeks after enrollment and prior to treatment initiation: SF-36, EPIC, AUA-SI, regret scale, CES-D, MAX-PC, SWD, PSQ-18, CPS, DCS and trust scale. Demographics, health and family history, clinical covariates and cancer progression data will be collected at 3, 6, 12 and 24 month follow-up. Histological tumor grade Gleason score and PSA and annual Elixhauser comorbidity score [257-258] will be obtained from the Pennsylvania Integrated Clinical and Research Database (PICARD), a UPHS, Fox-Chase Cancer Center electronic database, and PVAMC administrative and patient HER database. Retention and survey administration: During enrollment, importance of active participation will be emphasized. All participants will complete self-administered surveys at baseline within 1-2 weeks after enrollment (prior to treatment initiation) and again 3,6,12 and 24 months post-enrollment (see Appendix for copies of instruments, consent and medical chart review form). Non-respondents will be contacted via telephone after 10 days. In case of non-response due to death, cause of death will be noted and the physician investigators will determine cause of death (PCa or non-PCa related). The PCa conjoint analysis task, DCS, CPS and trust scale will be administered at baseline only, immediately after diagnosis of PCa and before treatment decision. D.2.4 Outcomes Assessment: D.2.4.1 As part of Specific Aim 2, following instruments will be used to measure preferences for participation in treatment decision, decision conflict and physician trust for both intervention group and the usual care control group at baseline, immediately after treatment decision, but prior to initiation of treatment. D.2.4.1.1 Control Preferences Scale (CPS): The CPS assesses the role that patients want to play and perceive playing in treatment decisions [259]. It consists of five sort-cards to assess different roles in decision making, ranging from a fully active to a fully passive role. This survey will be administered at baseline only. D.2.4.1.2 Decision Conflict Scale (DCS): The DCS is based on a conceptual framework of decision conflict, which is a state of uncertainty about which course of action to take. This scale is well studied in cancer area and has good psychometric properties [260]. We will administer this survey at baseline (before treatment). D.2.4.1.3 Patient Trust-Wake Forest Physician Trust Scale: This 10-item instrument is based on a multi-dimensional conceptual model of trust and measures trust in physicians and other health care providers [128-130]. Compared with previous scales, it showed improved internal consistency and variability [129, 131-132, 261]. Trust is measured by the sum of the 10 item scores, ranging from 10 to 50, with a higher score indicating higher trust [129, 131-132, 261]. D.2.4.2 As part of Specific Aim 3, the following outcomes will be measured for both intervention group and the usual care control group after initiation of treatment. D.2.4.2.1 Treatment choice: We will obtain data on primary and secondary treatments received, such as active surveillance, RP, RALP, EBRT, BT or PT via self report and verified from medical chart review. . D.2.4.2.2 Satisfaction with Decision (SWD): The SWD scale measures satisfaction with healthcare decisions. It was developed in the context of postmenopausal hormone-replacement therapy decisions. The six-item scale has excellent reliability (Cronbachs alpha = 0.88) [262]. D.2.4.2.3 Regret scale: Regret represents the unsettling feeling of having made a poor choice of treatment, persistent doubt, and a wish to change one's mind. The Regret scale is defined by three items that assess (1) the mans wish that he could change his mind about the kind of treatment he has received, (2) his feeling that he would be better if he had chosen the other treatment, and (3) whether he is bothered by the fact that other men received very different treatments for their PCa [33]. This scale exhibited good psychometric properties and has been extensively studied [33, 174, 263-265]. D.2.4.3 Following objective and subjective outcome measures will be assessed at baseline and at each post-treatment follow-up period (3,6,12 and 24 months) for intervention group and usual care control group. D.2.4.3.1 Biochemical recurrence: We will define progression of PCa as a change in PCa stage to an advanced stage or PSADT, post treatment [11, 44-45, 55, 160, 203]. We will obtain PSA data at baseline, prior to treatment, and post treatment at three months interval for 18 months. A PSA value of greater than 0.2 ng/ml indicates disease recurrence for surgery patients. For radiation therapy patients, we will adopt the Houston /Phoenix definition of the current PSA nadir + 2 ng/mL, with date of failure determined at call as the biochemical recurrence after radiation therapy [11, 44-45, 55, 160, 203]. Any treatment within six-month of diagnosis will be considered as adjuvant (review by investigators Drs. [name], [name], and [name]). D.2.4.3.2 Medical complications: We will identify complications that occur during either index or subsequent PRINCIPAL INVESTIGATOR (LAST, FIRST, MIDDLE): [name] PCORI Research Plan: Research Strategy 11 hospital admissions within 30 days of treatment [266]. Alibhai, et al. (2005), has grouped complications after RP into seven mutually exclusive categories: cardiac; respiratory; genitourinary; wound or bleeding; vascular; miscellaneous medical; and miscellaneous surgical [266]. Similarly, a list of complications for each treatment type will be developed by literature review and the physician investigators and consultants. D.2.4.3.3 Generic HRQoL- Medical Outcome Study Short Form: HRQoL data will be obtained using the Medical Outcome Study Short Form (SF-36) a multi-

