patients in decision (measured using CPS) using multi-nominal regression model to adjust for observed covariates. Then we will examine if these associations vary across intervention and usual care control groups. We then will repeat the model with other independent variables (decision conflict and trust). Next, we will test the association denoted by path c (direct effect of DCS, CPS, and trust on outcomes). For continuous outcomes (HRQoL, AUA-SI, MAX-PC, CES-D, SWD, and PSQ-18), we will compute area under the curve (AUC) for each measure for each patient. We will analyze AUC summaries with univariate linear models. In our main analysis we will analyze the series of functional status measures using linear mixed models that predict the outcome from time, independent variables and their interaction. We will repeat the analyses described for path c, this time by including treatment received in the models. We will test if the observed effects of DCS, CPS or trust on outcomes will be weaker after controlling for treatment. These analyses will be performed within and between groups (intervention and usual care controls). Specific Aim 3: Hypothesis: Prostate cancer patients in the intervention group undergoing conjoint analysis-value clarification exhibit improved treatment choice, satisfaction with decision, lower regrets, and improved objective and subjective outcomes. Analysis for Specific Aim 3 uses intent-to-treat approach: all randomized participants will be included regardless of whether they drop out of the intervention or study. Analysis will involve comparison of the primary outcomes between intervention and usual care control groups. Improved treatment choice is operationalized as the likelihood of low-risk PCa patients receiving active surveillance than active treatment, and will be compared between intervention and usual care control group. To allow for different trajectories of the outcome measures and to afford flexibility in making contrasts within participants over time and across participants, while simultaneously controlling for potential confounders, we propose the participant-specific or mixed effects linear model, in which the mean outcome depends on fixed covariates and random effects. The primary fixed effects will be indicators for intervention group and hospital. We will also stratify the analysis by type of treatment. The random effects represent the unobserved factors that lead to variation of the individual participants outcome. Random intercepts for each participant permit modeling of natural variation across participants at baseline. In addition, random slopes or random effects for the trajectory of each participant over time, allow for variation of each participant about a mean, overall trajectory across all participants. Although less robust to model misspecification, the mixed effects paradigm offers special flexibility in longitudinal data when exposures vary over time and when dropout and missed visits lead to unbalanced groups. The target of inference is the participant-specific response to treatment over time. At each time point of interest, we will estimate from the fitted model the difference from baseline in outcome for the treatment and control groups and test the difference between these differences. Both univariate and multivariate results will be reported in terms of Wald test, point estimates, and 95% confidence intervals. Specific Aim 4: Hypothesis 4: Prostate cancer patients whose treatment is more concordant with their values markers will experience improved subjective and objective outcomes. This specific aim s for intervention group only. We will analyze the association of the concordance between stated individual preferences and actual treatment received with objective (PCa recurrence and complications), subjective (HRQoL, psychological wellbeing, SWD, and satisfaction with care) outcomes, across treatment groups, adjusting for covariates. Association between the value markers (profiles) and measures of outcomes and personal and clinical characteristics: The value markers will be studied for their relationship with socio-demographic and clinical characteristics. We will also assess the association of value markers with outcomes. We will perform logistic regression with outcomes as the dependent variable and dummy variables for the utility-based profiles obtained earlier as independent variables. We will perform this evaluation with and without adjusting for patient attributes in the logistic model. For each case (adjusting and not adjusting for patient attributes), the evaluation of association between these profiles and outcomes will be based on a likelihood ratio test of the set of odds ratios corresponding to the dummy variables of the profiles. Additionally, we will perform a sequence of pair wise tests of comparisons of the profiles in terms of the proportion of type of treatment received based on the Holms multiple comparisons approach. This procedure is hierarchical in that it will identify the utility-based profile at the start of the process before making other comparisons, thus protecting the Type I error from additional comparisons. Specifically, Holms approach tests each pair-wise comparison in ascending order of p-values. Successively larger p-values have less rigorous alpha. The sequential Holm tests terminate after the first non-significant comparison so no subsequent comparison is significance. Concordance and its assessment: Understanding and respect for the patients preference and values is the main aspect of concordance [69, 73]. Thus a first step in concordance involves the physician extracting and understanding the patients view, followed by an agreement between the physician and patient regarding a management plan that integrates their views. There exist many definitions of concordance. For the purpose of this study, we operationalized concordance as agreement between a patients value markers and the attributes (or characteristics) of the treatment that

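### Aim 3 would test satisfaction with decision and regret as change from baseline, but neither scale has a valid baseline under any timing the protocol gives

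*Combined protocol and SAP*

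**What the plan says.** The Aim 3 hypothesis (Analysis Plan, Specific Aim 3) is that intervention patients "exhibit improved treatment choice, satisfaction with decision, lower regrets, and improved objective and subjective outcomes". For repeated scores the plan gives a linear mixed model with fixed effects for arm and hospital and random intercepts and slopes. Its test, at each visit of interest, is stated as "we will estimate from the fitted model the difference from baseline in outcome for the treatment and control groups", followed by a test of the difference between those two differences. SWD and regret are not excepted, and no other Aim 3 test is written for them.

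On when the two scales are collected, the protocol says two things:

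- D.2.4.2, repeated under Primary outcome variable(s), covers treatment choice, SWD and regret: "the following outcomes will be measured for both intervention group and the usual care control group after initiation of treatment". A separate list, D.2.4.3, holds the measures taken at baseline as well as at follow-up. Neither scale is on it.
- D.2.3, repeated under Procedures, has surveys mailed one to two weeks after enrolment and "prior to treatment initiation: SF-36, EPIC, AUA-SI, regret scale, CES-D, MAX-PC, SWD, PSQ-18, CPS, DCS and trust scale". Both scales are on that list.

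On content, the first regret item (D.2.4.2.3) concerns "the mans wish that he could change his mind about the kind of treatment he has received". For the other scale, D.2.4.2.2 says: "The SWD scale measures satisfaction with healthcare decisions".

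On where baseline falls relative to the decision, the text is also divided. D.2.3 says the conjoint task, decision conflict, control preferences and trust measures "will be administered at baseline only, immediately after diagnosis of PCa and before treatment decision". The recruitment text in D.2.1.2 likewise puts the intervention arm's conjoint task and other surveys ahead of the decision. D.2.4.1 places the baseline for control preferences, decision conflict and trust just after the decision, though still before treatment. D.2.2.1 has conjoint results given to intervention patients, their families and physicians before the decision.

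**The concern.** A change score needs a starting value that measures the same thing as the later value and is untouched by the intervention. A man cannot regret a treatment he has not had, nor rate a decision he has not made. If he has made it, the intervention has already had its chance to act. These two scales are among the outcomes closest to what a values-clarification exercise can alter. A test that cannot be computed, or that subtracts an irrelevant or already affected value, weakens the trial there. It also leaves the analyst to choose a replacement after the data are in.

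**Working it through.** **Step 1: each reading of the timing.**

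- *Both scales collected only once treatment has begun (D.2.4.2).* There is no baseline value, so the stated contrast cannot be computed.
- *Regret collected in the pre-treatment mailing (D.2.3, Procedures).* Every baseline described comes before treatment, so an item about treatment received has no sensible answer.
- *SWD collected before the decision (D.2.1.2).* There is no decision to rate, so the value carries little or no information about the later score.
- *SWD collected after the decision but before treatment (the D.2.4.1 timing, which the mailing window allows).* The item can be answered, but the intervention arm has already received its conjoint results. If the arms differ by d0 at this baseline and by d at follow-up, the contrast estimates d − d0, while d is the effect wanted. The documents give no value for d0.

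**Step 2: does the mixed model absorb this?** Not as written. With baseline as an outcome row, visit-specific arm means and complete data, the difference of differences equals the raw change-score comparison.

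**Step 3: the plan's own power figure (Accrual section).** Inputs: 360 per arm, 10% loss, hence 324; intra-class correlation 0.3; four follow-ups; two-sided 0.05; 80% power; SD 8 to 14 for PCI and SF-36.

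- SD of a four-visit mean at SD 8: 8 × √((1 + 3 × 0.3)/4) = 8 × √0.475 = 5.51.
- Detectable difference: 2.802 × 5.51 × √(2/324) = 1.21, against the stated 1.2. Power at 1.2 is 0.79.

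The figure reproduces at the lowest SD in the range (at SD 14 the detectable difference is 2.12) and with no baseline subtracted. It therefore does not describe the Aim 3 change contrast, and it concerns neither SWD nor regret.

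**Step 4: what subtraction costs at one visit (illustration).** Assume equal variances at baseline and follow-up, correlation r between them, and a follow-up comparison with 80% power. Then Var(change)/Var(follow-up) = 2(1 − r), and power = Φ(2.802/√ratio − 1.960). The detectable difference with 324 per arm is 2.802 × √(2 × ratio/324) SD; for follow-up scores alone it is 0.220 SD.

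| r | Ratio | Φ argument | Power | Detectable difference (SD) |
|---|---|---|---|---|
| 0 (assumed) | 2.0 | 2.802/1.414 − 1.960 = 0.021 | 51% | 0.311 |
| 0.1 (assumed) | 1.8 | 2.802/1.342 − 1.960 = 0.128 | 55% | 0.295 |
| 0.3 (plan's intra-class correlation) | 1.4 | 2.802/1.183 − 1.960 = 0.408 | 66% | 0.260 |
| 0.5 (break-even) | 1.0 | 2.802 − 1.960 = 0.842 | 80% | 0.220 |

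This covers added noise only. It does not cover the loss of d0 in the post-decision reading of SWD.

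**The case against.** **The contrast may not be meant for these scales.** The sentence is generic. It cannot govern every Aim 3 outcome, since treatment choice, recurrence and complications have no baseline difference in a linear model. The split between D.2.4.2 and D.2.4.3 suggests that the baseline contrast was meant for the D.2.4.3 measures. This is a fair reading, and it turns the defect into a missing exception rather than a declared invalid test. It does not remove the defect: no other test is written for either scale, and the mailing list would supply a baseline value to subtract. Regret is also absent from the opening summary of primary outcomes, but it is in the Aim 3 hypothesis.

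**A reader might infer that no man has made his decision at baseline.** The documents do not support that. D.2.4.1 puts one version of baseline after the decision, and the mailing is tied only to enrolment and to the start of treatment. For SWD under that version the harm is attenuation, not noise. Regret is unaffected, because every version precedes treatment.

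**The power loss can look worse than it is.** The fall to 51% occurs at a true effect of 0.220 SD, which the plan does not name as a target. At 0.5 SD, the low end of what it calls clinically relevant for PCI and SF-36, the change contrast at r = 0 gives 0.5/√(4/324) = 4.50, hence power Φ(4.50 − 1.96), about 99%. That stands, although the plan does not say that 0.5 SD applies to these scales. A reader might also infer a larger loss by averaging the four follow-ups, but Aim 3 tests visit by visit, so that is not the plan's contrast.

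**Conclusion.** The point holds in a limited form. The test Aim 3 supplies cannot validly be applied to SWD or regret. Regret has no usable baseline on any reading. SWD has none, or one taken before there is a decision to rate, or one that follows the intervention.

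The size cannot be fixed from the documents, which give no SD, target effect or power for either scale. The fall from 80% to 51% or 66% is an illustration at one visit. It rests on equal variances, on the assumed 80% starting power, and on correlations of 0 (assumed) and 0.3 (borrowed from the plan's power section). The conclusion about validity rests on the text and does not depend on those figures.

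**What to change.** In Specific Aim 3, exempt SWD and regret from the difference-from-baseline contrast. Compare the randomised arms directly on follow-up scores at 3, 6, 12 and 24 months, in the same mixed model with arm, visit, arm-by-visit and hospital, and with no baseline outcome row.

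Reconcile D.2.4.2 with the mailing list in D.2.3 and Procedures, so that it is clear whether either scale is collected before treatment.

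Follow-up visits are timed from enrolment, so a man may reach a visit with no decision or no treatment yet. State in advance how his scores are handled, in the same way in both arms.

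The cost is wording only, with no new data. Randomisation supports the comparison without a baseline. The small downside is that early visits may include some men for whom the items do not yet apply.

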size based on the observed differences in outcomes such as HRQoL (SF-36 and prostate cancer index, PCI) and cost of PCa care across groups. The primary outcome is HRQoL as measured by the SF-36 and PCI sub-scales. A change of 5 to 9 points on PCI is clinically meaningful [272]. Similarly, a difference of 7 points or more on the SF subscales is considered clinically meaningful [272, 275, 301]. Based on our prior research and that of Litwin et al [253, 272], the standard deviations for the PCI and SF-36 scales in samples of men with PCa mostly range from 8 to 14; hence standardized differences (SDs) of $7/14=0.5$ to $7/8=0.87$ will be clinically relevant. The power calculations for Aims 2-4 assume availability of 720 participants who are eligible for randomization into one of the two intervention groups. We assume a conservative intra-class correlation of 0.3 and 4 follow-up measures per subject. The sample size is adjusted to accommodate a 10% missing or dropout rate by 24 months based on rates over a similar period of time in previous studies [272, 275, 301]. We assume 80% power and two-sided level of significance of $\alpha = 0.05$. We have 80% power to detect a 1.2 point difference in PCI or SF-36 sub-scale. Within treatment type, the sample size is reduced to 60 per intervention arm. We have 80% power to detect a 3.0 point difference in sub-scale with 60 patients in each arm. Thus, we will have adequate power to detect differences between treatment groups [302]. Power for identifying utility based profiles and outcomes: We analyzed the levels of power for differences in outcomes between profiles defined by latent classes of attributes-specific utilities with a conservative allocation of subjects to each profile (25 in one vs. 10 in other profile) and less conservative allocation (35 in one profile vs. 35 in other profile) using a logistic model based comparison for a binary outcome (e.g. recovery of baseline HRQoL) with a 2-sided alpha of .0125 (Holms adjustment profiles). In the first allocation, the group difference of 0.56 yields 80% power; for the second allocation an effect size of 0.42 corresponds to power of 90. Thus, with our anticipated effect size of 0.51, we will have adequate power with $n=60$ in each group. (Adjusting for patient characteristics may reduce the effect sizes of the differences between profiles.)

Key inclusion criteria

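### Aim 3 tests the between-arm difference in change from baseline with no stated baseline adjustment or common baseline mean; adding one is an optional precision gain whose size the documents do not determine

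*Combined protocol and SAP*

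**What the plan says.** Analysis Plan, Specific Aim 3, describes an intention-to-treat mixed linear model. For each time point the plan is to "estimate from the fitted model the difference from baseline in outcome for the treatment and control groups and test the difference between these differences". On model terms it says: "The primary fixed effects will be indicators for intervention group and hospital". Each participant has a random intercept, and slopes are planned too: "In addition, random slopes or random effects for the trajectory of each participant over time". The section speaks in general terms of controlling for confounders. The list in D.2.4.4 covers disease severity, Gleason score, comorbidity and demographics, but not the baseline score of the outcome. No section sets the arms to a common baseline mean, and the form of time in the Aim 3 model is not stated.

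The sample-size text under Accrual supplies the inputs: "We assume a conservative intra-class correlation of 0.3 and 4 follow-up measures per subject"; "the standard deviations for the PCI and SF-36 scales in samples of men with PCa mostly range from 8 to 14"; 10% missing or dropout by 24 months; two-sided alpha 0.05. Its thresholds are "A change of 5 to 9 points on PCI is clinically meaningful" and "a difference of 7 points or more on the SF subscales is considered clinically meaningful". Its whole-trial claim is "We have 80% power to detect a 1.2 point difference in PCI or SF-36 sub-scale". It gives no random-slope variance and no intercept-slope covariance.

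On timing, D.2.3 and Procedures have the surveys mailed one to two weeks after enrolment and before treatment starts. The recruitment text has men already randomised to the intervention completing the conjoint task together with other surveys. Nothing fixes whether the baseline surveys come before the envelope is opened.

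**The concern.** In a randomised comparison, a between-arm difference in a baseline score taken before assignment is chance. A contrast of changes subtracts that chance difference in full and so carries the noise of the baseline measurement. The random intercept does not cure this: it places baseline among the responses, but an arm difference at baseline is still estimated and removed. Adjusting for the baseline score, or giving the arms one baseline mean, uses the same data more efficiently.

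At stake are the width of the intervals and the power for modest differences. The open wording also leaves the handling of baseline to be chosen later, possibly after the data are seen.

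**Working it through.** **Inputs.** Scale so that the baseline SD is 1. ICC 0.3 gives random-intercept variance 0.3 and residual variance 0.7. Visits are at 0, 3, 6, 12 and 24 months. n = 360 × 0.9 = 324 per arm. For a variance factor v, SE = SD × √(2v/324). Group-by-time terms are assumed, since a difference in changes needs them. Slope variances τ² (in SD² over 24 months) and intercept-slope correlations r are my assumptions.

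**1. The plan's 1.2 points.** A mean of four follow-ups with no baseline term has v = (1 + 3 × 0.3)/4 = 0.475. At SD 8 the detectable difference is 2.80 × 8 × √(2 × 0.475/324) = 1.21, and power at 1.2 is 79%. The stated figure therefore reproduces at SD 8, but for a different contrast from the one Aim 3 tests. At SD 14 the same formula gives 2.12.

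**2. Month 24, categorical time, no random slopes.** Planned change contrast: v = 2(1 − 0.3) = 1.40. Common baseline mean: v = 1 − 0.3² = 0.91. Reduction: 1 − 0.91/1.40 = 35%.

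**3. Month 24, linear time.** Let t = months/24. Its mean is 0.375 and its sum of squares about the mean is 0.625. Let c = r√(0.3τ²).

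- Planned: v = τ² + 0.7/0.625 = τ² + 1.12.
- Common baseline mean: v = τ² + 1.12 − (c − 0.42)²/0.5975, where 0.42 = 0.7 × 0.375/0.625 and 0.5975 = 0.3 + 0.7 × (0.2 + 0.375²/0.625).

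The term subtracted is a square, so the constraint cannot raise the variance. The gain vanishes as c approaches 0.42.

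| τ² | r | c | planned v | constrained v | reduction |
|---|---|---|---|---|---|
| 0 | – | 0 | 1.12 | 0.825 | 26% |
| 0.6 | −0.5 | −0.212 | 1.72 | 1.051 | 39% |
| 0.6 | 0 | 0 | 1.72 | 1.425 | 17% |
| 0.6 | +0.25 | 0.106 | 1.72 | 1.555 | 9.6% |
| 0.6 | +0.5 | 0.212 | 1.72 | 1.648 | 4.2% |
| 1.5 | +0.5 | 0.335 | 2.62 | 2.608 | 0.5% |

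**4. Power at alpha 0.05, planned versus constrained.** The planned SE at SD 14 is 14 × √(2 × 1.40/324) = 1.30 (categorical, no slopes) or 14 × √(2 × 1.72/324) = 1.44 (linear, τ² = 0.6).

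| Difference | categorical, no slopes | linear, τ² = 0.6, r = 0 |
|---|---|---|
| 5 points, SD 14 | 97% vs 99.7% | 93% vs 97% |
| 3 points, SD 14 | 64% vs 82% | 55% vs 63% |
| 1.2 points, SD 8 | 36% vs 52% | 31% vs 36% |

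At r = +0.5 instead of 0, the 3-point gain in the last column is only 55% to 57%. Planned power for 5 points at SD 14 is 88% at τ² = 1.0 and 80% at τ² = 1.5.

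**5. Bonferroni.** The Analysis Plan applies this correction but does not state the number of tests. As an illustration, with 4, 8 or 12 tests, power for 5 points at SD 14 goes from 91/87/84% to 99/98/97% (categorical, no slopes), or from 83/77/73% to 91/86/83% (linear, τ² = 0.6, r = 0).

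**6. Switching to categorical time at the same step.** The constrained categorical factor is (1 + 2c + τ²) − (0.3 + c)². At r = +0.5 and τ² = 0.6 it is 2.024 − 0.262 = 1.762, against 1.72 for the unadjusted linear plan: +2%. At τ² = 1.5 it is 2.767 against 2.62: +6%. At ICC 0.7 without slopes it is 1 − 0.49 = 0.51 against 0.3/0.625 = 0.48: +6%.

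**The case against.** The strongest reply is that the gain may be negligible in the model actually planned. Random slopes are in the plan, and with a positive intercept-slope correlation and linear time the reduction falls to a few percent or less. Power at the plan's own thresholds is high without adjustment: for 7 points at SD 14 it exceeds 99% at τ² = 0.6 and is about 98% at τ² = 1.5. All of this stands, and it is why the point is optional.

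It can also be said that the general wording on confounders would allow the baseline score. It would, but it does not call for it.

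A third reply is that fixing the order of surveys and assignment at three hospitals is not trivial. That is fair, although the planned change contrast depends on the same order.

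Three stronger readings are tempting, and the documents support none of them.

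- A reader might infer that 35% is the gain. That figure needs a model without random slopes.
- A reader might infer that Aim 3 is underpowered, because the month-24 change contrast has only 31% to 36% power for 1.2 points at SD 8. But 1.2 points is far below the 5 and 7 points that the plan calls meaningful.
- A reader might infer that the baseline scores are contaminated by assignment. The documents leave the order open; they do not say that the surveys follow assignment.

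**Conclusion.** The omission is real and the planned test is valid, provided baseline is unaffected by assignment. This is an optional efficiency improvement to the whole-trial Aim 3 comparison. With the time form held fixed, the constraint does not raise the large-sample variance. Its benefit depends on the ICC, the slope variance, the intercept-slope covariance and the time form, and only the ICC is given. The figures also assume 324 men per arm with complete data. The range found, from about 0.5% to 39%, reflects the assumed slope values and is not a bound. For differences the plan calls meaningful, the gain is small at alpha 0.05. It becomes material for smaller differences, or once the Bonferroni correction is applied.

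**What to change.** In the whole-trial Aim 3 model, keep whatever time form is planned and state it. Model baseline and the four follow-ups as responses, and constrain the arms to a common baseline mean. This keeps men whose baseline survey is missing, in line with the intention-to-treat statement. If the baseline score is used as a covariate instead, state how a missing baseline is handled.

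Apply this to SF-36, EPIC, AUA-SI, PSQ-18, CES-D and MAX-PC. Leave out regret and satisfaction with decision, which rate a choice already made. Do not impose the constraint in analyses by treatment received, because those groups form after randomisation. Do not move to categorical time as part of this change: against a linear plan it can cost more precision than the adjustment gains.

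State that baseline surveys are completed before assignment is known. If that cannot be assured, do not impose the constraint.

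The cost is SAP wording, with no extra patients or measures. Securing the survey order is an operational change, since the surveys are now mailed after enrolment, but the planned contrast needs it as well.
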